10.3 Analysis of Adverse Events

In the SURF study, only device-related or procedure-related adverse events and serious adverse events (SAEs) will be collected from procedure through discharge. After discharge, only neurological SAEs will be collected. Additional information for Symptomatic Intracranial Hemorrhage and Ischemic Stroke will be collected on Event of Interest case report forms.

Frequency counts and percentages will be provided for all reportable adverse events and broken down as well based on relationships to the device and procedure. Reportable adverse event data will be listed for each patient, including the type of event/verbatim term, start date, seriousness, action taken, outcome, and causality (if appropriate). The onset of adverse events will also be shown relative (in number of days) to the date of procedure.

The specific categories analyzed will be those that are reported by at least three (3) percent of the patients. As there is no CEC for this study, all adverse events will be reported based on the assessment from the clinical study sites.

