10.2 Sample Size Estimation for the Primary Outcome

Approximately 800 patients will be enrolled in this post market study with estimated 10% attrition at final follow-up. Assuming an observed rate of 89% (641/720) for the endpoint of Raymond-Roy I-II at follow-up, the sample size precision is greater than $\pm 3\%$ for this endpoint (95% CI: 87% to 91%). Assuming an observed rate of 2.8% (22/800) for the primary endpoint of device-related serious adverse events up to 7 days or discharge, the sample size precision is greater than $\pm 1.5\%$ for this endpoint (95% CI: 1.6% to 3.9%). Assuming an observed rate of 8.9% (71/800) for the primary endpoint of serious adverse events at 24 hours post procedure, the sample size precision is greater than $\pm 2.5\%$ for this endpoint (95% CI: 6.9% to 10.9%). These precision estimates are based on the normal approximation binomial 95% confidence intervals and SMART Registry interim results (data on file at sponsor). Hence, the sample size provides an adequate level of precision for these primary endpoints.

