10.11 Analysis of Adverse Events

All adverse events will be summarized by showing the number and percent of subjects which report the event. Events will also be reported by relationship to the procedure or device. Adverse events judged as probably or definitely related to the SMART COIL System will be analyzed as device-related.

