Approximately 800 patients will enroll in this post-market study, resulting in 720 patients who achieve final follow-up after 10% anticipated attrition. This sample size provides adequate precision to estimate the primary effectiveness and safety endpoints.

Primary Endpoint	Assumption for Observed Rate ^[1]	95% CI ^[2]	Precision
Adequate occlusion defined as Raymond-Roy Occlusion Class I and II at final follow-up	89% (320/360)	86% to 92%	Greater than $\pm 3.5\%$
	89% (401/450)	86% to 92%	Greater than $\pm 3\%$
	89% (481/540)	86% to 92%	Greater than $\pm 3\%$
	89% (561/630)	87% to 91%	Greater than $\pm 3\%$
	89% (641/720)	87% to 91%	Greater than $\pm 3\%$
Device-related SAE up to 7 days or discharge	2.8% (11/400)	1.1% to 4.4%	Greater than $\pm 2\%$
	2.8% (14/500)	1.4% to 4.2%	Greater than $\pm 1.5\%$
	2.8% (17/600)	1.5% to 4.2%	Greater than $\pm 1.5\%$
	2.9% (20/700)	1.6% to 4.1%	Greater than $\pm 1.5\%$
	2.8% (22/800)	1.6% to 3.9%	Greater than $\pm 1.5\%$
SAEs within 24 hours post-procedure	9.0% (36/400)	6.2% to 11.8%	Greater than $\pm 3\%$
	9.0% (45/500)	6.5% to 11.5%	Greater than $\pm 2.5\%$
	8.8% (53/600)	6.6% to 11.1%	Greater than $\pm 2.5\%$
	8.9% (62/700)	6.8% to 11.0%	Greater than $\pm 2.5\%$
	8.9% (71/800)	6.9% to 10.9%	Greater than $\pm 2.5\%$

^[1] Set at SMART CLP 10023 Registry interim observed results (data on file at sponsor)

^[2] Two-sided 95% Wald normal approximation binomial proportion confidence interval

3 Interim Analysis

As there will be no interim analyses for the purpose of terminating the study early for success or futility, alpha adjustments will not be made to the confidence intervals in the final analysis. However, interim analysis may be performed for the purpose of publication or regulatory submission of SURF results.

4 Analysis Populations

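### The 3% cut-off on adverse event categories in SAP 10.3 conflicts with protocol 10.11 and with the SAP's own preceding paragraph, and would drop rarer serious and device-related categories from the tables

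*Combined protocol and SAP*

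**What the plan says.** Protocol 10.11 states the rule without a threshold: "All adverse events will be summarized by showing the number and percent of subjects which report the event". It adds a breakdown by relationship to procedure or device.

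SAP 10.3 makes the same commitment in its second paragraph: "Frequency counts and percentages will be provided for all reportable adverse events", again split by relationship to device and procedure. It also promises a listing: "Reportable adverse event data will be listed for each patient, including the type of event/verbatim term, start date, seriousness", followed by action taken, outcome and causality.

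The next paragraph of SAP 10.3 then says: "The specific categories analyzed will be those that are reported by at least three (3) percent of the patients". It makes no exception for serious or device-related events, and it defines neither what a category is nor what being analysed means.

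The planned size is given in SAP Section 2: "Approximately 800 patients will enroll in this post-market study, resulting in 720 patients who achieve final follow-up after 10% anticipated attrition". The planning rates for the two primary safety endpoints are in protocol 10.2: "Assuming an observed rate of 2.8% (22/800) for the primary endpoint of device-related serious adverse events up to 7 days or discharge" and "Assuming an observed rate of 8.9% (71/800) for the primary endpoint of serious adverse events at 24 hours post procedure".

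**The concern.** SAP 10.3 gives two instructions that cannot both govern the same table. A programmer who follows the later and more specific sentence would leave every category below 3% out of the adverse event tables.

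A frequency filter is also a poor fit for this study. Such filters usually trim common, non-serious, unrelated events. Here those events are never collected: protocol 7.6.1 and SAP 10.3 restrict collection to SAEs and device- or procedure-related events up to discharge, and to neurological SAEs afterwards. The filter can therefore act only on events that the study chose to collect because they matter.

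The study's stated objective includes demonstrating safety. What is at stake is whether a reader can see, type by type, how often the rarer serious or device-related complications occurred.

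**Working it through.** **Inputs**
- Cut-off: 3% of patients (SAP 10.3).
- N = 800 enrolled; the ITT population is all enrolled patients (SAP Sections 2 and 4.1).
- Device-related SAE to day 7 or discharge: 22/800 (protocol 10.2, SAP Section 2).
- Any SAE within 24 hours: 71/800 (same places).
- Interval method: "Two-sided 95% Wald normal approximation binomial proportion confidence interval" (SAP Section 2, table footnote).
- True rates for single categories: not given in the documents, so those used in steps 4 and 5 are assumptions.

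**1. The plan's own figures.** Wald interval: p ± 1.96 × √(p(1 − p)/n).
- 22/800 = 2.75%; half-width 1.96 × √(0.0275 × 0.9725/800) = 1.13 points; interval 1.62% to 3.88%. The plan states 1.6% to 3.9%.
- 71/800 = 8.88%; half-width 1.96 × √(0.08875 × 0.91125/800) = 1.97 points; interval 6.90% to 10.85%. The plan states 6.9% to 10.9%.

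Both agree.

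**2. The cut-off as a count.** 0.03 × 800 = 24. A category reported by 23 patients (23/800 = 2.88%) is left out.

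**3. Cut-off against the assumed total of device-related SAEs, for each scenario in SAP Section 2**

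| N | Assumed patients with any device-related SAE | Patients needed for 3% |
|---|---|---|
| 400 | 11 | 12 |
| 500 | 14 | 15 |
| 600 | 17 | 18 |
| 700 | 20 | 21 |
| 800 | 22 | 24 |

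In every row the total over all types is below the cut-off. If the assumed count is observed, no category consisting only of these events can reach it.

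**4. Chance that a category is analysed.** Exact binomial, P(X ≥ 24) with n = 800; chance of at least one case, 1 − (1 − p)^800.

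| Assumed true rate | Expected patients | P(X ≥ 24) | P(X ≥ 1) |
|---|---|---|---|
| 1% | 8 | 0.0000032 (0.0003%) | 0.9997 |
| 1.5% | 12 | 0.0013 | above 0.9999 |
| 2% | 16 | 0.035 | above 0.9999 |
| 2.5% | 20 | 0.21 | above 0.9999 |

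The study would almost certainly observe events in a category at 1% to 2%, and the rule would almost always leave that category out.

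**5. SAEs within 24 hours.** A single category needs 24/71 = 34% of the affected patients. Suppose the 71 patients split equally over k categories, so that each has rate 71/(800k). The chance that a given category reaches 24 is then 0.98 for k = 2, 0.50 for k = 3, 0.09 for k = 4 and 0.01 for k = 5. Some serious categories could pass; with four or more of similar size, a given one probably would not.

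**The case against.** The strongest reply is that there is no contradiction: SAP 10.3 already repeats the protocol's commitment, and the 3% sentence only selects categories for some further summary. That would reconcile the texts, but the SAP describes no further summary, and the terms on which the reading depends are undefined. The sentence needs rewording on either reading.

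A second reply is that much safety reporting is untouched. This stands. The two primary safety endpoints (SAP 10.1), the secondary ones including major ipsilateral stroke (SAP 10.2), and deaths (SAP 10.4) are reported with confidence intervals at any frequency, and every reportable event is listed by patient. A reader might infer that the rule hides rare serious events altogether; the documents do not support that. The listings, however, carry verbatim terms, and a reader would have to code and count them to obtain a category rate.

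A third reply is that comparing 22 with 24 proves less than it seems. This stands in part:
- The cut-off counts all patients reporting a category, with no split by seriousness or relatedness. A device-related SAE in a category that reaches 3% overall would still be covered.
- The 22 is an assumed count. At a true rate of 2.75%, chance alone would bring the pooled total to 24 or more with probability 0.36. At the earlier registry's 16/500 = 3.2% for procedural device-related SAEs (protocol Section 1), the expected total is 25.6 and the probability 0.65. That concerns all types pooled, however. Two equal categories at 11/800 each would reach 24 with probability about 0.0004.

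It is also tempting to say that every serious category would be lost, or that the rule defeats what the study is sized to detect. Neither holds. With 71/800 planned within 24 hours, a category with about a third of those patients passes, and later SAEs add to the counts. The sample size rests on three aggregate proportions, not on event categories.

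**Conclusion.** The concern holds in a limited form. The 3% sentence conflicts with protocol 10.11 and with the paragraph before it in SAP 10.3. Followed literally, it removes from the category tables any category with fewer than 24 of 800 patients, with no exception for serious or device-related events.

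Two statements of size can be supported. At the planned count, categories made up only of device-related SAEs to day 7 or discharge all fall short. A category with a true rate of 1% to 2% would be analysed with probability between about 0.0003% and 3.5%. The first rests on the plan's assumed count being the one observed; the second rests on illustrative rates.

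No endpoint, estimate or confidence interval changes. The loss is confined to category-level tabulation, but that is a real loss in a study whose objective includes demonstrating safety.

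**What to change.** Delete the 3% sentence from SAP 10.3. Alternatively, confine it to non-serious adverse events related to neither device nor procedure. Under the present collection rules that leaves it almost nothing to act on, so deletion is the simpler course.

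In either case, add a statement that all SAEs and all device- or procedure-related adverse events are tabulated by category, with counts and percentages and no frequency threshold, in line with protocol 10.11. Say also what a category is, so that the tables can be programmed without interpretation.

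The cost is a sentence or two in the SAP and longer tables. No additional data are needed.

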10.4 Analysis of Deaths

Survival estimates will be used to evaluate the time-to-event using the Kaplan-Meier product-limit method for deaths through 365 days. With the date of procedure set at day 0, any event occurring on or before day 365 will be included. If clinical assessment is missing for a patient who has not died, the patient will be censored at the last follow-up date. Patients who are alive at day 365 will be censored at day 365. The time to death will be plotted with 95% confidence intervals.

Additionally, the frequency and percentage of deaths for any reason (all-cause mortality) will be presented with the two-sided 95% Wald confidence interval.

11 Pooling Across Centers

Analyses will be presented using data pooled across centers. The primary and secondary effectiveness and safety endpoints will be presented by study site to assess any potential site effects.

Pooling analyses will be conducted across study sites on the primary effectiveness and primary safety endpoints. Fisher's exact test (univariate analysis) and stepwise binary logistic regression

on study site, adjusted for key baseline and other appropriate variables (multivariate analysis), will be used. The multivariate results will take precedence in testing for site heterogeneity.

To assess the validity of pooling North America (US/Canada) and Europe sites, logistic regression models will be used for the primary effectiveness and primary safety endpoints. Stepwise multivariate binary logistic regression models with geographic location (North America (US/Canada versus Europe), study site, and a subset of key baseline and procedural predictors will be used for each primary endpoint to test for heterogeneity across geographic locations.

Wald odds ratios of the treatment effects for geographic location and study site will be presented with two-sided p-values to test whether the odds ratios equal 1. Centers enrolling three or fewer patients will be eliminated from all pooling analyses.

12 Missing Data and Imputation Methods

The primary analysis will be data as observed, in which results are reported using the data that are available without imputing missing values.

As sensitivity analyses, the primary effectiveness and primary safety endpoints will be recomputed using the ITT population after imputing missing data:

- Imputation using baseline scores (run for primary effectiveness only)
- Imputation using the worst clinical scenario, assuming the subject was assessed as Raymond-Roy Class III at the time of final follow-up (effectiveness) or experienced a primary safety event (safety)
- Imputation using the best clinical scenario, assuming the subject was assessed as Raymond-Roy Class I and II at the time of final follow-up (effectiveness) or did not experience a primary safety event (safety)

13 Changes to Planned Analyses

All changes to this Statistical Analysis Plan (SAP) will be documented in a revised SAP or the clinical study report.

14 References

Agresti A (2013). *Categorical data analysis*. John Wiley & Sons.

CLP SURF – SURF: A Prospective, Multicenter Study Assessing the Embolization of Neurovascular aneurysms using WAVE™ Extra Soft coils, a part of the Penumbra SMART COIL® System. 13669 protocol.

Meyers PM, et al (2010). Reporting standards for endovascular repair of saccular intracranial cerebral aneurysms. *American Journal of Neuroradiology*, 31(1), E12-E24.

CLP SMART – A prospective, multicenter registry assessing the embolization of neurovascular lesions using the Penumbra SMART COIL® System. 10023 protocol.

van Amerongen MJ, et al (2014). MRA versus DSA for follow-up of coiled intracranial aneurysms: a meta-analysis. *American Journal of Neuroradiology*, 35(9), 1655-1661.

Woodward K and Forsberg DA (2013). AngioSuite: an accurate method to calculate aneurysm volumes and packing densities. *Journal of Neurointerventional Surgery*, 5(Suppl 3), iii28-iii32.

15 Revision History

Version	Prepared By	Description of Changes
1.0	[name]	Initial Release
2.0	[name]	Updated number of sites, subgroup analysis, and pooling analysis to reflect global site enrollment under protocol revision C Updated sample size and endpoint definitions
3.0	[name]	Added sample size scenarios to Section 2. Sample Size

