The interim analysis from the first 500 consecutive subjects enrolled included cerebral aneurysms (90.6%, 451/498), of which 31.0% were ruptured; arteriovenous malformations (1.4%); fistulae (4.6%); and other lesions (3.4%)[39]. At admission, 70.8% of subjects were female, and the mean age was 60.0 ± 13.3 years. Aneurysms were small (87.7%), large (12.1%), and giant (0.2%), with 64.2% (265/413) having a wide neck.

The median time of fluoroscopic exposure was 36.5 minutes (IQR 24.0-56.0). Stent-assisted coiling was performed in 29.8% of patients, whereas balloon-assisted coiling was performed in 19.4% of patients. For all aneurysms, the median packing density was 29.5% (IQR 21.4-38.3). For all subjects, adequate occlusion at immediate post-procedure was achieved for 97.6% (483/495). In aneurysm subjects, Raymond I or II was achieved in 79.7% (354/444) of patients at immediate post-procedure, and 88.6% (124/140) at one-year follow-up. The retreatment rate through one-year follow-up was 3.8% (6/157).

Procedural device-related SAEs were observed in 3.2% (16/500) of patients. Mortality rates were 0.4% (2/496) within 24 hours of intervention and 11.4% (21/185) after 24 hours; no deaths were device-related. One-year follow-up data collection is ongoing.

Initial results suggest that the SMART COIL System achieves adequate embolization in a variety of neurovascular lesions. The clinical evidence has shown that coiling is a safe and durable alternative treatment option for suitable subjects. The SURF study will provide additional clinical evidence on the safety and efficacy of the WAVE™ Extra Soft coil (WAVE) for the treatment of cerebral aneurysms.

2. Penumbra SMART COIL System with WAVE Extra Soft Coil

The WAVE Extra Soft Coil is part of the SMART COIL System offered by Penumbra, Inc. and is specifically designed as a filling and finishing coil. WAVE may be used with other SMART Coils that have different sizes and properties: SMART Plus Standard, Standard, Soft, and Extra Soft. The specific coil that is most suitable is determined largely by the morphology of the aneurysm and coil properties needed at various packing stages. The SMART COIL System is designed for endovascular embolization in the neuro and peripheral vasculature. Intended users for this device are physicians who have received appropriate training in interventional radiology.

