16.4.9 Aneurysm Size

Aneurysm size should be reported in millimeters in 3 dimensions as well as categorical taxonomy:

- Small Neck: < 4 mm
- Wide Neck: ≥ 4 mm or a dome to neck ratio of less than 2 mm
- Small Aneurysms: ≤ 5 mm at its largest diameter
- Medium Aneurysms: 6 – 14 mm at its largest diameter
- Large Aneurysms: 15 mm – 24 mm at its largest diameter
- Giant Aneurysms: ≥ 25 mm at its largest diameter

[figure not shown]

[figure not shown]
Figure 2. Aneurysm Sizing

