8.5 Handling of Multiplicity

There will be no adjustment for multiplicity in SURF study reporting.

9 Subgroup Analysis

The following subgroup analyses will be performed for all primary and secondary effectiveness and safety endpoints using the ITT population:

- **Adjunctive technology used during treatment:** Balloon, Stent, Other, None
- **Age at time of informed consent (years):** < 65, \geq 65
- **Sex:** Female, Male
- **Ethnicity:** Hispanic or Latino, Not Hispanic or Latino
- **Race:** American Indian or Alaska Native, Asian, Black or African American, White, Other
- **Site country:** North America (US/Canada), Europe
- **Target aneurysm location:** Extradural ICA, ICA, ACA, MCA, Posterior Circulation, Other
- **Target aneurysm size:** Small (\leq 5 mm at its largest diameter), Medium (6 to 14 mm at its largest diameter), Large (15 to 24 mm at its largest diameter), Giant (\geq 25 mm at its largest diameter)
- **Target aneurysm status:** Ruptured, Unruptured
- **Target aneurysm anatomical location:** Bifurcation, Sidewall, Other
- **Neck width:** Small-Neck (< 4 mm Neck Width), Wide-Neck (\geq 4 mm Neck Width or Dome-to-Neck Ratio (defined as the maximum of dome width, depth, and height divided by neck width) $<$ 2)
- **Target aneurysm previously treated:** Previous Treatment at Admission, No Previous Treatment at Admission

Descriptive statistics and two-sided 95% Wald confidence intervals will be presented for each subgroup.

10 Safety Analysis

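### SAP 11 promises adjusted odds ratios for both region and study site, but region cannot be estimated beside fixed site terms

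*Combined protocol and SAP*

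**What the plan says.** SAP 11 plans two pooling analyses of the primary endpoints.

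The first concerns study site. It uses Fisher's "exact test (univariate analysis) and stepwise binary logistic regression" on site with covariate adjustment, and adds: "The multivariate results will take precedence in testing for site heterogeneity".

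The second concerns region. Its stated purpose is to assess whether North American and European sites may be pooled. The models are "Stepwise multivariate binary logistic regression models with geographic location (North America (US/Canada versus Europe), study site, and a subset" of baseline and procedural predictors, one for each primary endpoint. The output is stated without condition: "Wald odds ratios of the treatment effects for geographic location and study site will be presented with two-sided p-values". A further rule applies to both analyses: "Centers enrolling three or fewer patients will be eliminated from all pooling analyses".

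SAP 9 defines the regional subgroup by site country, with levels "North America (US/Canada), Europe". SAP 11 does not say that region is forced in, that site is random or nested in region, what the entry and stay levels are, or what is reported if region is not selected.

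**The concern.** Region is a property of the site. A model with a separate fixed effect for every site already contains all the information on region, so nothing remains from which to estimate a regional effect. The SAP nevertheless lists both terms together and promises an odds ratio and p-value for each.

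At stake is the only covariate-adjusted comparison of the two regions in the plan. The SAP revision history shows that the pooling analysis was updated when the study opened to global sites, and the documents foresee use of the results in regulatory submissions. An analysis that may not produce its stated output should be corrected before database lock.

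The site analysis has a related weakness. Device-related SAEs are rare and the number of sites may be large, so many sites will have no event. Yet the regression takes precedence over Fisher's exact test, which zero cells do not harm.

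**Working it through.** **Inputs from the documents.** About 800 patients at up to 60 sites (SAP 1). Planning assumptions in SAP 2: 641/720 adequately occluded, hence 720 − 641 = 79 failures; 71/800 with an SAE within 24 hours; 22/800 with a device-related SAE. Two regions, defined by site country (SAP 9). SAP 11 gives no figure of its own to reproduce.

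**1. Degrees of freedom for region given site.** Let D_j indicate site j and let R indicate Europe. Each site is in one region, so R = sum of D_j over the European sites, exactly. Then df(region | site) = rank[1, site, region] − rank[1, site].

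- 60 sites: 60 − 60 = 0, with the sites split 45/15 or 30/30.
- 40 sites: 40 − 40 = 0.
- 20 sites: 20 − 20 = 0.

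Region alone has 1 df; with 60 sites, site given region has 58. Order of entry does not matter. If region enters first, its coefficient after site enters is only a contrast between the reference site of each region, and it changes with the choice of reference. Dropping sites with three or fewer patients leaves every remaining site in one region. This result needs no assumption beyond fixed site effects.

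**2. The two readings of SAP 11.**

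- *Region and site always kept, selection only among covariates.* Site is always present, so the adjusted regional odds ratio is never identified.
- *Region and site both subject to selection.* If site is selected, region has 0 df. If neither is selected, the final model has no regional term. Only if region is selected and site is not does the promised odds ratio exist, and it then ignores clustering by site.

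**3. Illustration of the second reading.** Forward entry by score tests was simulated for occlusion (720 patients, 60 sites of unequal size split 45/15, no other covariates, 4,000 runs per row). The entry level, between-site SD (logit scale), split and site sizes are all assumptions.

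| True occlusion by region | Site SD | Entry level | Neither | Region only | Site in model |
|---|---|---|---|---|---|
| 89% / 89% | 0 | 0.05 | 90.5% | 4.7% | 4.9% |
| 89% / 89% | 0.5 | 0.05 | 55.4% | 5.3% | 39.3% |
| 89% / 89% | 0.5 | 0.15 | 31.0% | 8.0% | 61.1% |
| 90.5% / 84.5% | 0 | 0.05 | 40.0% | 54.3% | 5.7% |
| 90.5% / 84.5% | 0.5 | 0.05 | 24.6% | 34.1% | 41.4% |
| 90.5% / 84.5% | 0.5 | 0.15 | 9.9% | 29.7% | 60.4% |

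The odds ratio in the last three rows is (0.905/0.095)/(0.845/0.155) = 1.75. Only the Region only column yields the promised output.

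**4. Sites without a device-related SAE.** At most 22 sites can hold 22 affected patients. At least 60 − 22 = 38 of 60 sites, or 30 − 22 = 8 of 30, have none. At such a site the fitted log odds diverge, with or without covariates. A Wald odds ratio between it and a site with events is therefore not finite.

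**5. What the data can support.** With 71 or 79 events, region plus three single-df covariates leaves 71/4 = 17.8 or 79/4 = 19.8 events per term. For device-related SAEs, the region-only log odds ratio has approximate SE = sqrt(sum of 1/cell). At a 50:50 patient split this is sqrt(2/11 + 2/389) = 0.43, so the 95% CI spans a factor exp(1.96 × 0.43) = 2.3 either side. At 70:30 the SE is 0.47 and the factor 2.5; at 85:15 they are 0.60 and 3.3.

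**The case against.** A reader might infer that the plan contains no test of region at all, or that the data decide whether one exists. The documents do not support that. Under stepwise selection region can be tested at entry, and non-selection is itself a finding. What is never or only conditionally available is the adjusted odds ratio. The entry-step test ignores clustering by site and is not the Wald odds ratio and p-value that SAP 11 promises, so the defect remains in this narrower form.

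The unconditional promise of odds ratios for both terms, and the description of the first analysis as a regression on site, also suggest that both terms are always kept. On that reading the selection frequencies fall away. The aliasing does not; it becomes certain. Site could instead have been meant as a random effect, but the SAP does not say so, and odds ratios per site point the other way.

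The frequencies in the table also deserve caution. They move with the entry level and between-site SD, neither of which is in the documents. Where the regions truly do not differ, selecting neither term is the right conclusion about region, not a failure.

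Finally, the practical weight is modest, and this stands. Protocol 10.1 makes all analyses descriptive. SAP 11 presents pooled results regardless and tabulates endpoints by site. SAP 9 gives unadjusted rates with confidence intervals by region. No pooling decision depends on the test.

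**Conclusion.** The concern holds. Given fixed site effects, which odds ratios per site imply, SAP 11 cannot deliver an adjusted regional odds ratio from any model that contains site: region then has 0 df. The output is never available if both terms are kept, and available only when region is selected without site if both are subject to selection. No reliable frequency can be attached to the second case.

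The site analysis of device-related SAEs has a separate fault. If the planned 22 events occur, at least 38 of 60 sites, or 8 of 30, yield non-finite Wald odds ratios against sites with events, while the regression is given precedence over a valid exact test. Sixty is the maximum number of sites; the actual number is not in the documents.

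A reader might infer that the pooled primary results are unsound. They are not affected: they are descriptive proportions that do not depend on these models. The SAP should be corrected, but the effect is confined to the pooling assessment.

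**What to change.** 1. **Regional model, occlusion and 24-hour SAEs.** Replace stepwise selection with one pre-specified logistic model: region forced in as a fixed effect, site as a random intercept, and a short list of baseline and procedural covariates that the sponsor names before database lock, limited by the 71 to 79 expected events. Report the regional odds ratio with its 95% CI. If the site variance is estimated as 0, say so and report the same model without the random intercept. This fallback is needed: in simulations with assumed between-site SDs, the estimate was 0 in 13–21% of runs at SD 0.5 and 39–44% at SD 0.3.
2. **Regional model, device-related SAEs.** Use a Firth-penalised model with region only, and state that it ignores clustering by site and has low precision.
3. **Site heterogeneity.** Do not report individual site Wald odds ratios. For device-related SAEs, let the planned Fisher's exact test be the site test, with a Monte Carlo p-value if needed. For the other two endpoints, report the between-site SD with a CI and a likelihood-ratio test of the site variance, and let this be the multivariate result that takes precedence.
4. **Interpretation.** State for all endpoints that a non-significant result or a zero variance estimate is not evidence that pooling is valid.

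The cost is SAP wording and standard SAS procedures (GLIMMIX, and LOGISTIC with the FIRTH option), with no new data. Individual site odds ratios are given up; the by-site tables remain.
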